10.5. Masking

This is an open-label study and the site and subjects will not be masked to the assessment device. Three sets of trial lens frames will be prepared using the refraction values from the 3 devices, including the EyeQue VisionCheck, phoropter, and autorefractor. During the study, the subjects and site personnel performing the BCVA assessments will be masked to the refraction values that are used to prepare each of the trial lens frames. Masking regarding the trial lens frames will

be maintained throughout the study by use of separate site personnel to prepare the frames and perform the BCVA assessment.

If the site personnel performing the BCVA assessments or a subject is unmasked, the subject must be discontinued from the study. Additionally, the sponsor and or designee must be notified.

27

11. STUDY SCHEDULE AND PROCEDURES

11.1. Study Schedule

The study schedule can be found in Appendix 1. Detailed information on study assessments is provided in Section 12.

11.2. Study Visits

11.2.1. Visit 1

All study-related procedures, including screening, will be completed in 1 visit.

11.2.1.1. Screening Procedures

The subject will complete the following assessments and procedures at Screening:

- Informed consent
- Demographics/medical history/concomitant medication review
- Slit-lamp biomicroscopy
- Laser retinal scan or fundoscopy; images will be taken during this procedure
- Optical coherence tomography; images will be taken during this procedure
- Tonometry (non contact)
- Ishihara color test
- Cover test
- Retinoscopy; results will be used as a basis for further refinement by phoropter refraction
- Refraction values (sphere, cylinder, axis) for OD and OS using the phoropter
- Best corrected visual acuity (LogMAR scores for OD, OS, and OU) assessed using the phoropter refraction values and ETDRS eye chart; subjects are eligible to participate in the study only if their vision can be corrected to 20/20 (LogMAR 0.0)

All eye procedures will be completed without dilation using standard procedures.

11.2.1.2. Testing procedures

Once eligibility is confirmed, the subject will be enrolled and proceed with study testing procedures.

The following testing procedures and assessments will be completed:

- Refraction values (sphere, cylinder, axis) for OD and OS using the autorefractor
- Measurement of pupillary distance using the autorefractor; pupillary distance will be used for preparation of trial lens frames

• Refraction values (sphere, cylinder, axis) for OD and OS using the EyeQue VisionCheck; all subjects will be trained on how to use the EyeQue VisionCheck device prior to initiating testing

In order to obtain refraction values using the EyeQue VisionCheck, the subject will be required to take 1 practice test followed by a minimum of 3 saved tests for each eye using the EyeQue VisionCheck device and mobile app. After completion of a set of tests (1 test for each eye), the subject may elect to save or discard that set of tests. They may choose to discard for any reason which may include not following instruction, pressing the wrong button in error, etc. Each test consists of the subject looking through the VisionCheck device and using the app controls to fully overlap red and green bars at 9 different angles. After completion of all tests (1 practice test and 3 saved tests with each eye), the refraction values will be displayed on the mobile app. If the EyeQue system determines that the overall test results are unreliable, subjects may have to complete 3 additional tests per eye before the system may be able to provide refraction values. Subjects will not be allowed to complete more than 6 saved tests are unreliable, no values will be provided.

- Best corrected visual acuity (LogMAR scores for OD, OS, and OU) assessed using the ETDRS eyechart and trial lens frames produced from:
 - Phoropter refraction values
 - Autorefractor refraction values
 - EyeQue VisionCheck refraction values
 - *Subject and assessor will be masked to the refraction values used to produce the trial lens frames
- Subject preference regarding each of the trial lens frames
- Adverse event recording

11.2.1.3. Early Termination

Unless otherwise indicated, subjects will be discontinued from the study if any of the following events occur:

- The subject wants to withdraw from the study.
- The subject is non-compliant with the study protocol
- The subject has no refraction values produced with the EyeQue VisionCheck device
- At the investigator's discretion, continued testing is medically contraindicated.

The reason(s) for premature discontinuation from the study will be recorded.

12. STUDY ASSESSMENTS

12.1. Efficacy Assessments

Results from all efficacy assessments will be recorded on the appropriate eCRF pages.

12.1.1. Best Corrected Visual Acuity

Best corrected visual acuity will be measured using trial lens frames prepared based on the refractive error measured by each device including the EyeQue VisionCheck, phoropter, and autorefractor. Best corrected visual acuity will be assessed using the ETDRS eye chart. For each subject, BCVA logMAR scores will be collected for OD, OS, and OU for each of the 3 trial lens frames.

12.1.2. Refraction Values

Refraction values (sphere, cylinder, axis) for OD and OS will be recorded for each subject using the EyeQue VisionCheck, phoropter, and autorefractor. The refraction values will be used to prepare 3 sets of trial lens frames.

12.1.3. Subject Preference

Subjects will be asked which of the 3 trial lens frames affords them the best overall visual acuity. Subjects will be asked to order the trial lens frames by which frame(s) provides the best vision. A tie is permitted when a subject feels 2 or more frames afford indistinguishable differences in visual acuity.

12.2. Safety Assessments

All subjects who enter the study will be assessed for safety. Safety will be monitored by observation of and direct inquiry regarding AEs during the study visit.

12.2.1. Adverse Events

All AEs, ADEs, and SAEs will be collected from the start of informed consent through the end of the study visit. Details regarding AE definitions, collection, recording, and reporting are found in Section 12.3.

12.2.2. Demographics and Medical History

Demographic information relating to the subject's sex, age, race, ethnicity, and medical history will be collected during the Screening procedures and recorded on the appropriate eCRF page.

12.2.3. Concomitant Medications/Therapies

All concomitant medications/therapies will be recorded in the subject source documentation. The prohibited and/or allowed concomitant medications/therapies for the study are discussed in Section 10.1.

12.3. Adverse Events

12.3.1. Adverse Events, Adverse Device Effects, and Serious Adverse Events

Adverse events will be recorded throughout the study and will be coded using the Medical Dictionary for Regulatory Activities (MedDRA).

The investigator is responsible for the detection and documentation of AEs and ADEs. For all AEs/ADEs, the investigator must pursue and obtain information adequate to determine the outcome of the AE and to assess whether the AE meets the criteria for classification as an SAE requiring immediate notification to the sponsor or its designated representative.

12.3.1.1. Definitions of Terms

12.3.1.1.1. Adverse Events

Any undesirable clinical occurrences observed in subjects during an investigational clinical study. In addition to novel events, an AE may be an exacerbation of a pre-existing medical condition that was present before the subject was assigned to a treatment group.

12.3.1.1.2. Serious Adverse Event

Adverse events considered serious are those that result in one or more of the following

- Death
- Immediately life-threatening

NOTE: The term "life-threatening" refers to an event in which the subject was at immediate risk of death at the time of the event. It does not refer to an event that hypothetically might have caused death if it were more severe.

- Result in hospitalization or prolongation of an existing hospitalization
- Persistent or significant incapacity or substantial disruption of the ability to conduct normal life functions.
- Results in a congenital anomaly/birth defect
- Important medical events that are not fatal, life-threatening, or require hospitalization may be considered serious when, based upon appropriate medical judgment, they may jeopardize the subject and may require medical intervention to prevent one of the outcomes listed in this definition.

Non-serious adverse events are all other adverse events not deemed serious.

12.3.1.1.3. Adverse Device Effect

An adverse device effect is an AE that is suspected to be related to the device. Adverse device effects can be either anticipated, which means that they have been previously identified in this protocol or the investigator's brochure, or unanticipated.

12.3.1.1.4. Unanticipated Adverse Device Effect

An unanticipated ADE (UADE) is any serious adverse effect on health or safety, any lifethreatening problem or death caused by, or associated with a device, if that effect, problem, or death was not previously identified in nature, severity, or degree of incidence in the application; or any other unanticipated serious problem associated with a device that relates to the rights, safety, or welfare of subjects.

12.4. Severity of Adverse Events

The study site will grade the clinical severity of AEs experienced by study participants as either:

- Mild: Causes no limitation of usual activities
- Moderate: Causes some limitation of usual activities
- Severe: Prevents or severely limits usual activities

It is important to distinguish between serious and severe AEs. Severity is a measure of intensity whereas seriousness is defined by the regulatory criteria in Section 12.3.1.1.2.

12.5. Relationship to Test Article

An investigator's causality assessment is the determination of whether there exists a reasonable possibility that the investigational device caused or contributed to an AE and must be provided for all AEs (serious and non-serious).

The sponsor's determination of attribution will be used for reporting to the appropriate health authorities. The relation of an AE to study participation will be determined using the descriptors and definitions provided in Table 1.

| Not Related | The AE is clearly/most probably caused by other etiologies such as participant's underlying condition, therapeutic intervention or concomitant therapy, or the delay between administration and the onset of the AE is incompatible with a causal relation, or the AE started before administration (screening phase). Therefore, there is not a reasonable possibility that the AE was caused by the investigational device. |
|-------------|--|
| Related | There is a reasonable possibility that the AE was caused by the investigational device. The expression "reasonable possibility" is meant to convey in general that there are facts (evidence) or arguments to suggest a causal relationship. |

The investigator should decide whether, in his or her medical judgment, there is a reasonable possibility that the event may have been caused by the investigational device. Any AE that is suspected to be related to the EyeQue VisionCheck, phoropter, or the autorefractor will be classified as an ADE.

12.6. Recording Adverse Events

All AEs, regardless of relatedness to the use of the test article, are to be recorded on the appropriate AE page (either serious or non-serious) in the eCRF throughout the study. All adverse effects during the study will be documented in the subject's medical record. This information will then be transcribed on the AE page of the eCRF by designated study personnel. Required information includes a description of the event, date of onset, date of resolution, the action taken to manage the AE, the subsequent outcome, and severity.

Adverse events resulting from concurrent illnesses, reactions to concurrent medications, or progression of disease states must also be reported.

All AEs/ADEs must be followed to adequate resolution or stabilization. If the AE/ADE has not resolved or stabilized by the time the subject completes the single study visit, the investigator will follow the status of the subject's AE/ADE for at least 7 days beyond the subject's final study visit, unless directed otherwise by the sponsor.

12.7. Reporting SAEs and Unanticipated Adverse Device Effects

For reporting of SAEs and UADEs, the following process ensures compliance with 21 CFR 812 and International Conference on Harmonisation (ICH) guidelines. Investigators and other study center staff must inform Rho Product Safety representatives of any SAE/UADE that occurs (whether or not attributable to the study drug) in the study within 24 hours of when he or she becomes aware of the SAE/UADE. It is the investigator's responsibility to ensure that SAE/UADE reporting procedures are followed appropriately. In addition, the investigator must ensure that these events are entered on the SAE/UADE eCRF via Rave electronic data capture (EDC) or via paper form, if Rave EDC is unavailable. The form will be entered into EDC or faxed to the Rho Product Safety personnel within 24 hours. The following variables will be recorded for each AE: verbatim/AE description, time and date for AE start and stop, maximum intensity, seriousness, causality rating, whether or not the AE caused the subject to discontinue, and the outcome.

Medical Monitor and Emergency Contact Information:

Rho, Inc. Medical Monitor

Email: [contact]

Serious Adverse Event Reporting Contact Information: Rho, Inc. Safety Group Email: [contact]

Serious Adverse Event Help Line: [name] Serious Adverse Event Fax Line: [name]

The investigator is responsible for informing the IRB of SAEs and UADEs as per local requirements, as well as according to applicable regulations.

12.8. Reporting SAEs and Unanticipated Adverse Device Effects to Health Authorities

The sponsor will forward all reportable SAEs/UADEs to the appropriate regulatory authorities and participating investigators according to 21 CFR 812 and any other applicable regulations.

12.9. Medical Emergency

In a medical emergency requiring immediate attention, study center staff will apply appropriate medical intervention, according to standards of care.

An investigator shall notify the Medical Monitor and the reviewing IRB of any deviation from the investigational plan to protect the life or physical well-being of a subject in an emergency. Such notice shall be given as soon as possible, but in no event later than 1 business day after the emergency occurred. Except in such an emergency, prior approval by the sponsor is required for changes in or deviations from a plan. All deviations must be documented.

13. STATISTICS

13.1. Power and Sample Size Determination

Approximately 200 subjects will be enrolled in this study to achieve a minimum of 100 evaluable subjects to assess the effectiveness and safety of the EyeQue VisionCheck. The initial cohort included 39 subjects; therefore, approximately 160 additional subjects will be enrolled in the study. Based on prior study data, rejection of non-inferiority bounds of 0.1 LogMAR (one line) and 0.05 LogMAR (one-half line) would require approximately 10 and 40 subjects, respectively, with 90% power on the BCVA from the resulting lens from each approach. This assumes the devices are roughly equivalent and the standard deviation (SD) is 0.077; these data are based on a previous version of the EyeQue VisionCheck device tested against an autorefractor. The proposed sample size has been inflated to allow for the possibility that a larger standard deviation will be observed in the current study, as well as to allow for comparisons within each stratum. A software error in the EyeOue app was identified and the algorithm for the EyeQue app was updated with more stringent parameters which may also impact the number of evaluable subjects. Due to the updates to the parameters, there may be additional subjects for which EyeQue VisionCheck refraction values are not produced, leading to an increase in the number of subjects that will not be evaluated for the primary endpoint. Of the approximately 160 additional subjects that will be enrolled in the study, it is anticipated that approximately 60 subjects will not be evaluable due to failing screening or not having refraction values produced with the EyeQue VisionCheck. Additionally, the larger sample size provides a sufficiently robust database for investigations of the secondary outcomes and descriptions of the EveQue VisionCheck's performance characteristics.

13.2. Analysis Populations

Two analysis populations are defined for this study.

Modified Intent to Treat Population: All subjects that perform BCVA for trial frames with test lenses based on both phoropter and EyeQue VisionCheck.

Safety Population: All subjects that meet the screening criteria and are enrolled in the study.

After enrollment in this study was initiated, a software error was identified in the EyeQue app used with the EyeQue VisionCheck. The software error was corrected and the algorithm for the EyeQue app was updated. An initial cohort of 39 subjects was enrolled in the study prior to these changes being implemented. Due to these EyeQue app updates, this initial cohort of 39 subjects will be excluded from the analysis populations and any safety information for these subjects will be listed separately.

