13.4. Safety Analyses

13.4.1. Adverse Events

Adverse events, ADEs, UADEs, and SAEs will be reported with counts and percentages. Adverse events that can be associated with a particular device will be reported separately from those without clear attribution. Adverse events will be coded using MedDRA terminology. A subject experiencing more than 1 instance of an event will be counted only once for that event. Analyses will be repeated for each age stratum including ages 30 through 65 and ages 45 through 65. Unanticipated ADEs will be flagged in the by-subject listings of all AEs.

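### The Safety Population leaves out the initial 39 subjects with no safety-related reason, so their adverse events will be listed but will enter no planned count or percentage

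*Combined protocol and SAP*

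**What the plan says.** Section 13.2 begins "Two analysis populations are defined for this study": the modified intent-to-treat (mITT) population and the Safety Population. The second is defined as follows: "Safety Population: All subjects that meet the screening criteria and are enrolled in the study".

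The same section reports that a software error in the app was found after enrolment had begun, that it was corrected, and that the algorithm was updated. Citing these updates, it states that "this initial cohort of 39 subjects will be excluded from the analysis populations and any safety information for these subjects will be listed separately". Since only two populations exist, the exclusion covers both. The synopsis says the same.

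Section 13.4.1 sets the safety summary: "Adverse events, ADEs, UADEs, and SAEs will be reported with counts and percentages". It also plans by-subject listings. It specifies no summary or denominator for the 39.

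Three other places bear on the point:
- Section 6.4 sets the safety objective as a comparison of VisionCheck with the phoropter and the autorefractor.
- Section 12.5 classes an event suspected to be related to any of the three devices as an ADE.
- Section 12.2 says that everyone who enters the study is assessed for safety.

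**The concern.** The exclusion conflicts with the population's own definition. Subjects who met the criteria and were enrolled belong to the Safety Population, and the next paragraph removes 39 of them.

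An algorithm change is a good reason to keep the 39 out of the efficacy analysis, because their lenses came from a different version of the software. The plan does not explain why the same reason should apply to safety. Section 9.4 attributes the potential effects (such as headache, dizziness, eye irritation and periorbital infection) to the device, to the comparators or to the procedure, and notes that VisionCheck touches the skin around the eye. An app error gives no reason to drop phoropter and autorefractor exposure, whatever the error was.

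At stake is how the safety objective is answered. Events in the 39 would be visible in a listing but would be in neither the numerator nor the denominator of any rate.

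**Working it through.** **Inputs (all from Section 13.1, except the exclusion itself, which is in 13.2)**
- Planned enrolment: "Approximately 200 subjects will be enrolled in this study to achieve a minimum of 100 evaluable subjects".
- Split: "The initial cohort included 39 subjects; therefore, approximately 160 additional subjects will be enrolled in the study".
- Expected losses among the 160: "approximately 60 subjects will not be evaluable due to failing screening or not having refraction values produced". The split between screen failures and subjects without values is not given.

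**Step 1. The plan's own total.** 39 + 160 = 199, which agrees with approximately 200.

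**Step 2. Share of planned enrolment left out of the safety rates.** 39/199 = 19.6% (39/200 = 19.5%).

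**Step 3. Share of exposures.** Let s be the number of screen failures among the 160, from 0 to 60. Subjects who used the device but obtained no values were exposed and stay in the Safety Population. Assuming that all 39 were exposed, the share is 39/(199 − s):
- s = 0: 39/199 = 19.6%
- s = 60: 39/139 = 28.1%

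**Step 4. Precision when no events are seen.** The one-sided 95% upper bound on an event rate is 1 − 0.05^(1/n).

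| Screen failures among the 160 | Without the 39 | With the 39 |
|---|---|---|
| none | n = 160: 1.85% | n = 199: 1.49% |
| all 60 | n = 100: 2.95% | n = 139: 2.13% |

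The second row applies only if every one of the 60 is a screen failure. The plan does not say so, and it names absent refraction values as the other cause.

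**Step 5. Effect on the rate table.** Take one ADE among the 39, none among the later subjects, and s = 0. The planned table shows 0/160 = 0%. Tabulated by app version it shows 1/39 = 2.6% and 0/160 = 0%, and pooled 1/199 = 0.5%.

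**Step 6. How likely an event in the 39 would be.** The plan gives no event rate, so the true rate p is an assumption. The chance of at least one event is 1 − (1 − p)^39: 32% at p = 1%, 55% at p = 2% and 86% at p = 5%.

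**The case against.** The best case for the plan is that the app and the cloud platform are two of the three components of the investigational device (Section 9.1), so an app update is a device change. Subjects work the test through the app. An unreliable result can lead to three further tests per eye, and Section 13.1 says that the updated parameters are more stringent. The update could therefore lengthen device use. Trial lenses made from the faulty app's values might also differ from later ones. On this view, rates limited to the updated version are the relevant ones, and the choice is stated openly. The plan also has no safety hypothesis, no safety-based sample size and no planned confidence bound for events, and Section 9.4 regards the study as one of nonsignificant risk.

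Much of this stands. It supports showing the versions separately. It does not support giving one version no counts or denominator, and it does not reach the comparator devices.

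A reader might also infer four stronger things that the documents do not support:
- *That the error affected refraction output and not exposure.* The error is never described. Only the later algorithm update is linked to whether values are produced.
- *That all 39 used the device.* They are called enrolled, and Section 7.1 has enrolled subjects go on to testing. But Section 13.1 counts screen failures among the 160 to be enrolled, so the word is used loosely.
- *That events in the 39 will be missing from the report.* A separate listing is planned, and the collection and expedited reporting rules do not exempt these subjects. The events are uncounted, not hidden.
- *That the later safety denominator is about 100.* That is the evaluable number for efficacy. It equals the safety denominator only if all 60 are screen failures.

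**Conclusion.** The point holds as a gap in the safety summary. Section 13.2 and the synopsis remove 39 enrolled subjects from a population whose definition includes those who met the criteria, and no safety-related reason is given. The listing keeps their events on record, but no planned rate includes them.

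The size is 19.6% of planned enrolment. The range of 19.6% to 28.1% of exposures rests on all 39 having been exposed and on the unstated split of the 60. The zero-event bounds are a reviewer's measure of precision. The loss is modest (1.85% against 1.49% if there are no screen failures) and changes no planned decision. The larger consequence is that the ADE table could read zero when an ADE had occurred. The efficacy exclusion is not in question. The change is worth making because it is specific and nearly free.

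**What to change.** 1. In Section 13.2 and the synopsis, limit the exclusion of the 39 to the mITT population, and state that those who meet the Safety Population definition remain in it.
2. In Section 13.4.1, tabulate AEs, ADEs, UADEs and SAEs, with denominators, in three columns: before the app update, after it, and pooled.
3. State how many of the 39 used each of the three devices, and describe the software error. If the sponsor has a safety-related reason for keeping the cohort apart, give it here.

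The cost is a sentence in each of two places and an extra set of table columns. The plan already commits to listing the safety information, so no new data are needed. The one drawback is that the pooled rate spans two app versions. The by-version columns make that visible and keep a separate rate for the updated version.
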